1.0 PROTOCOL SUMMARY AND/OR SCHEMA

Some patients treated with brain radiation therapy for tumors located in the head may develop new or increased enhancing mass lesions. These worsening lesions may represent radiation injury/necrosis or tumor progression. This study will examine the utility of MRI perfusion and FDG PET/CT to determine if the enhancing lesions represent radiation injury or tumor progression. Both MRI perfusion and FDG PET/CT scans are part of the standard of care for patients with indeterminate lesions after treatment. The purpose of this study is to prospectively enroll these patients in order to determine if MRI perfusion or FDG PET/CT performs better in predicting if a worsening enhancing brain lesion represents radiation injury or tumor progression. In addition the entire cohort analyses, subcohort analyses will be performed for patients belong to specific clinical scenarios and compared using an interaction test.

Prior to enrolling in the study, each patient will have a CT or MRI scan that shows an increasing indeterminate mass lesion. If the screening scan is a brain MRI perfusion, it can also function as the protocol intervention.

Screening (within 12 weeks of enrollment): Neurological and/or physical examination

Intervention: Brain MRI perfusion and PET/CT performed within 12 weeks of each other. Either MRI perfusion or PET/CT may be performed first. The first of the two scans should be performed within 12 weeks after the screening scan showing an increasing indeterminate mass lesion. If the screening scan is a brain MRI perfusion, it can also function as the protocol intervention. Imaging based diagnosis of radiation injury vs. worsening tumor will be rendered by a study neuroradiologist and by a nuclear medicine radiologist and entered into a secure database.

*Note that clinical reads of the MRI perfusion and PET/CT will be rendered as per the standard of care, usually within 24-48 hours after completion of the study. These reports get dictated in Powerscribe and then become part of the patient's electronic medical record.

Off study: Patients will remain on study until the completion of either the MRI perfusion or PET/CT that are within 12 weeks of each other. After one of these scans, the patient will have no active interventions and will be off study. Patients will obtain a standard of care brain MRI scan about every 2-3 months. These MRI scans will be used to track disease progression.

Follow up: Neurological/physical examination and brain MRI approximately every 2-3 months until death or 1 year after last MRI if lost to follow up. If clinical and radiological follow up is required, determination of the outcome (tumor progression vs. radiation injury) may require 6 months or more from the time of the intervention MRI perfusion and PET/CT scans.

2.0 OBJECTIVES AND SCIENTIFIC AIMS

The primary goal of the proposed study is to directly compare PET/CT with MRI perfusion in distinguishing between radiation injury and tumor progression. These are the two most commonly performed tests for possible radiation injury cases (MRI spectroscopy, diffusion imaging, and experimental PET/CT tracers trail far behind). There has been very little

comparative effectiveness research to determine an optimal imaging strategy, whether both are complementary and necessary, or whether one outperforms the other. This protocol will help us answer those questions, and may lead to dramatic changes in the way we and other institutions manage these diagnostic dilemmas. After the completion of radiation therapy and a follow-up MRI exam demonstrating a worsening enhancing brain lesion, patients will undergo both MRI perfusion and PET/CT exams. If the follow up MRI is a brain MRI perfusion, it will serve as both the screening scan and protocol intervention. In this case, patients will undergo only a PET/CT exam. The findings from each of these imaging studies will be used to predict whether the lesion represents tumor progression or radiation necrosis based on clinical follow-up and/or pathologic tissue sampling.

Primary Endpoint:

1. To assess the utility of PET/CT and MRI perfusion studies in predicting whether worsening enhancing brain lesions seen after radiation therapy represent radiation injury or tumor progression. This study will examine the role of these two imaging techniques in predicting diagnosis and treatment planning.

Exploratory Endpoint:

- 1. To assess the utility of PET and MRI perfusion studies in predicting tumor progression in patients with tumors with a history of brain radiation therapy receiving anti-angiogenic therapy (such as bevacizumab). Due to direct drug effects upon the vasculature, these tumors often show little or no enhancement despite clinical worsening and increasing non-enhancing abnormalities. The role of advanced imaging in determining progression in lesions that do not show increased enhancement has not been defined. In an exploratory fashion, we will enroll patients with tumors with a history of brain radiation therapy receiving anti-angiogenic therapy with suspected progression and increased nonenhancing lesions.
- 2. To assess the utility of MR diffusion imaging in predicting radiation injury or tumor progression. Water diffusion occurs independent of tumor blood flow (MRI perfusion) or glucose uptake (FDG PET/CT), and may also be a useful technique to evaluate worsening enhancing brain lesions.

3.0 BACKGROUND AND RATIONALE

Patients with tumors treated by brain radiation therapy may develop new and/or increased enhancing mass lesions within the spectrum of radiation injury. This frequently poses a diagnostic dilemma, as both radiation injury and worsening tumor may fulfill requirements for worsening disease when applying standard response criteria. These criteria usually rely on changes in size of the enhancing lesion on contrast brain MRI scans, which is the current imaging standard for the evaluation and follow up of patients with a history of brain radiation therapy.

Radiation therapy plays an important role in prolonging the survival of patients with primary (malignant gliomas) and secondary (metastases) malignancies of the head. Treatment protocols include administration of whole and/or partial brain radiation therapy as well as stereotactic radiosurgery. Toxicity of radiation therapy on the brain includes radiation-induced injury of healthy brain occurring months to years after treatment. ¹ Brain tolerance is related to the prescribed volume, dose, fraction and interval of radiation. Focal radiation injury may manifest with increased or new enhancing mass lesions that mimic worsening tumor. The term focal radiation injury is used here to include pseudoprogression in gliomas and radiation necrosis in both gliomas and metastases – these are related but distinct enhancing entities along a common continuum.

Pseudoprogression is the transient worsening of enhancing disease that occurs soon after completion of radiation therapy in patients with malignant gliomas. This occurs in approximately 31% of treated patients, and in 58% of patients with methylated O⁶-methylguanine-methyltransferase enzyme (MGMT) promoter status. ²⁻⁵ The increased and/or new enhancing mass lesions are due to early subacute potentiated radiation-induced tissue injury with inflammatory changes and necrosis. This is most common 1-3 months after radiation therapy, with lesions usually spontaneously stabilizing or improving by 6 months. In contrast to tumor progression, pseudoprogression has been associated with prolonged survival. ^{6, 7}

In contrast, radiation necrosis is an often irreversible process that develops many months to years after completion of radiation therapy. Patients develop increased or new enhancing mass lesions due to late subacute radiation-induced tissue necrosis, inflammatory changes and blood-brain barrier disruption. The lesions are also characterized by marked adjacent brain edema. Surgical resection is the most efficacious treatment. Patients may become dependent on steroids to control the enhancement and edema.

Enhancement is the combined result of tissue vascularity and accumulation of contrast in the extracellular extravascular space secondary to transendothelial diffusion or permeability. Tumors are characterized by neovascularization and angiogenesis with the formation of many new immature and leaky intratumoral blood vessels. While enhancement is usually interpreted to represent tumor, enhancement may also occur due to radiation injury from blood-brain barrier disruption without neovascularization. Rather than relying on contrast enhancement, we propose using two physiological imaging techniques to investigate the biology of the enhancing lesion(s): MRI perfusion and PET/CT.

No study has directly compared MRI perfusion with FDG PET/CT for the diagnosis of focal radiation injury. Although both are commonly performed, their comparative predictive value, sensitivity, specificity and indications remain uncertain. Many studies were performed using small patient cohorts and retrospective designs. We believe that the large numbers of neuro-oncology patients at MSKCC, and the large numbers of scans we (already) perform, leveraged with the benefits of a prospective protocol, will help overcome many of the limitations in the current literature. We hypothesize that MRI perfusion and PET/CT can prospectively predict radiation necrosis from tumor progression. Our goal is to directly compare the two techniques and determine if any particular clinical scenario (such as hemorrhagic lesions) would favor one over the other. Early diagnosis would help clinical decision-making, as the treatments for these two entities are very different.

The gold standard for the diagnosis of radiation injury is histopathology. This is an invasive technique, however, which may be limited by sampling error or may not be possible for inaccessible lesions in eloquent brain. A safe, noninvasive imaging biomarker to determine radiation injury is therefore desirable.

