3.2 Preliminary Data

MRI perfusion and PET/CT are already routinely performed for patients with tumors with a history of brain radiation at MSKCC. In 2010, we performed 1,474 MRI perfusion scans and 212 PET/CT scans, for determining radiation injury as well as a variety of other reasons that include for staging, preoperative planning, preradiation therapy planning, and treatment follow up. The vast majority of the MRI perfusion scans were performed using

the DSC technique, with very few (<50) performed using the potentially more robust DCE technique.

In a preliminary retrospective analysis, we identified 12 consecutive patients over a one year period with indeterminate enhancing lesions after radiation therapy who underwent DSC MRI perfusion, FDG PET/CT, and subsequent surgical resection with pathologic diagnosis (Hatzoglou V, Ulaner G, Beal K, Zhigang Z, Young RJ; Abstract 9012072, Radiological Society of North America, Chicago, IL, December 2010). Both primary (n=3) and secondary (n=9) brain neoplasms were included. Seven patients received stereotactic radiosurgery (SRS, 18-21 Gy), 2 patients whole brain radiation (35-52.5 Gy) and 3 patients partial brain radiation therapy (59.4-60 Gy). From the PET/CT scans, standardized uptake values (SUV) of the lesion and background were measured by a board-certified nuclear medicine radiologist and ratios (SUV_{ratio}) calculated. From the DSC MRI perfusion images, maximal relative cerebral blood volume (rCBV_{max}) values were measured by a board-certified neuroradiologist. P-values were obtained using bootstrap or permutation tests, and receiver operating characteristic (ROC) analyses and areas under curve (AUC) were calculated.

We found that the SUV_{ratio} had the highest predictive value (AUC=0.943) for tumor progression, although this was not statistically better than any perfusion metric (AUC=0.757-0.829). After excluding two patients with hemorrhagic lesions, the AUC of the perfusion metrics improved slightly to 0.917-0.938.

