This preliminary study found similar accuracy for PET/CT and MRI perfusion in distinguishing recurrent tumor from treatment necrosis. MRI perfusion performed better when patients with hemorrhagic lesions were excluded. These results have compelled us to develop a prospective trial, which will allow us to determine the optimal roles for PET/CT and MRI perfusion in the evaluation of patients with worsening enhancing lesions after treatment. We plan to perform DCE T1 perfusion instead of DSC T2* perfusion, as the DCE technique provides absolute measures of perfusion and permeability and is not limited by hemorrhage.

A systemic feature- or texture-based approach has been applied to PET scans in gynecological and head and neck cancers. This is similar to increasingly popular histogram analyses for other imaging data, 30 and has shown promise in treatment response analyses using multiparameter predictive models over single metrics such as simple SUV descriptive statistics. In a pilot study, correlation between feature-based predictive models and outcome improved by 14% in gynecological and 12% in head and neck cancers over SUV statistics.31

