11.2 Subcohort analyses

The patients will also be grouped according to the following clinical scenarios:

- 1) Gliomas after radiation therapy with increased or new enhancing lesions
- 2) Gliomas after radiation therapy in patients receiving bevacizumab or other antiangiogenic chemotherapy with increased or new enhancing and/or non-enhancing lesions
- 3) Metastases after radiation therapy with increased or new enhancing lesions
- 4) Metastases after radiation therapy who may be receiving bevacizumab or other antiangiogenic chemotherapy for systemic or brain disease

Although we anticipate similar changes in MRI perfusion and PET/CT for radiation injury (smaller values) vs. tumor (larger values) regardless of the clinical scenario, it is possible for different results to occur in gliomas vs. metastases, or initially treated vs. recurrent disease. Each scenario encompasses similar tumor types that are expected to receive similar standardized radiation therapy plans (in terms of dose, fractionation and schedule). For each subcohort of patients, we will determine the efficacy of MRI perfusion and PET/CT in predicting radiation injury vs. tumor progression in an exploratory fashion.

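### Hemorrhage is the clinical scenario that Section 3.0 names and part of the case for DCE, but the plan does not record hemorrhage status or analyse by it

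*Combined protocol and SAP*

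**What the plan says.** The background (Section 3.0) sets the aim of comparing the two techniques directly and of finding whether one is preferable in some settings: "determine if any particular clinical scenario (such as hemorrhagic lesions) would favor one over the other". No other setting is named in that sentence.

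The pilot (Section 3.2) covered 12 surgically resected patients imaged with DSC perfusion and FDG PET/CT. The AUC was 0.943 for the SUV ratio and 0.757-0.829 for the perfusion metrics. It then reports: "After excluding two patients with hemorrhagic lesions, the AUC of the perfusion metrics improved slightly to 0.917-0.938". The section draws the conclusion that "MRI perfusion performed better when patients with hemorrhagic lesions were excluded" and explains the move to DCE partly on the ground that "the DCE technique provides absolute measures of perfusion and permeability and is not limited by hemorrhage".

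In the analysis plan, Section 11.2 states: "The patients will also be grouped according to the following clinical scenarios". The four groups, also listed in Section 4.1, are glioma or metastasis, with or without anti-angiogenic therapy. Section 1.0 says these subcohorts will be "compared using an interaction test", and Section 11.3 adds an exploratory subcohort regression to look for heterogeneity.

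**The concern.** The one scenario that the goal names is absent from the list of scenarios to be analysed. Hemorrhage is also the only patient or lesion factor for which the pilot reports a change in perfusion performance. The pilot used DSC, so it says nothing about whether DCE removes the problem. If hemorrhage is neither recorded nor analysed, the trial will not report, as a planned result, whether bleeding in the lesion shifts the balance between PET and MRI, or whether the premise for DCE held. A later look would have to choose its definition of a hemorrhagic lesion with outcomes already known, among several metrics that Section 11.1 already places under false-discovery-rate control.

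**Working it through.** **1. Where hemorrhage appears.**

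| Place | Hemorrhage? |
|---|---|
| Goal in 3.0 | Yes, as the named example |
| Rationale for DCE in 3.1.2 and 3.2 | Yes, as one of several reasons |
| ROI placement in 4.2.1 | Yes, as tissue to avoid |
| Endpoints in 2.0 | No |
| Recorded measurements in 7.1 | No |
| Subcohorts in 4.1 and 11.2 | No |
| ANCOVA covariates in 11.1 (radiation dose, fractionation, schedule) | No |
| Regression in 11.3 | Only the existing subcohorts |

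**2. The plan's own power figure.** Section 11.1 gives a type II error of about 10% at effect size 0.5 for 150 patients, one-sided 5%. Scaling the stated 90 tumor and 42 injury patients to 150 gives 102 and 48. Then 0.5 / sqrt(1/102 + 1/48) = 2.857, and 2.857 - 1.645 = 1.212, so the type II error is 11.3%. At 0.7 it is 0.9%, against about 1% stated. The whole-cohort figure reproduces and does not depend on this point. The documents give no figure for hemorrhage.

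**3. What the pilot signal rests on.** With one lesion per patient and empirical AUCs, each AUC is a multiple of 1/(2 x n_tumor x n_injury).
- All 12 patients: 33/35 = 0.943, 26.5/35 = 0.757 and 29/35 = 0.829. Only a 5/7 split fits all three.
- The remaining 10: 22/24 = 0.917 and 22.5/24 = 0.938. Only a 4/6 split fits both.

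So the two excluded patients were one of each outcome. No PET AUC after the exclusion and no interaction test are reported.

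**4. Expected number of hemorrhagic patients.** Section 11.1 expects 90 + 42 = 132 patients with a diagnosis (its three outcome counts sum to 140, not 150; I use the counts as stated). The trial's prevalence is unknown. The pilot's 2/12 = 17% has an exact 95% CI of 2-48%. At 17%: 90/6 = 15 tumor and 42/6 = 7 injury, 22 in all. That leaves 75 and 35 non-hemorrhagic.

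**5. Precision of the contrast.** Assume an AUC of 0.8 for both tests in both groups. The Hanley-McNeil variance is [A(1-A) + (m-1)(a - A²) + (n-1)(b - A²)] / (mn), with a = A/(2-A) = 0.6667, b = 2A²/(1+A) = 0.7111 and A² = 0.64.
- Hemorrhagic, 15/7: (0.16 + 14 x 0.0267 + 6 x 0.0711)/105 = 0.00914, SE 0.096. The half-width for a single AUC is 1.96 x 0.096 = 0.19.
- Non-hemorrhagic, 75/35: (0.16 + 74 x 0.0267 + 34 x 0.0711)/2625 = 0.00173, SE 0.042.

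The PET and MRI AUCs come from the same patients. With correlation r between them, the half-width for the difference in AUC differences is 1.96 x sqrt[2(1-r)(0.00914 + 0.00173)]. This is 0.20 at r = 0.5 and 0.24 at r = 0.3. The documents give no r, so both values are assumptions.

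The same formula gives 0.16-0.19 at 30% prevalence and 0.38-0.44 at 5%. At 5% there are only about 4.5 tumor and 2.1 injury cases, and the approximation is optimistic. Simulation of the same contrast gives about 0.20-0.25 at 17%, 0.16-0.18 at 30% and above 0.4 at 5%.

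**6. Power for an interaction on one metric's mean.** At 17%: SE = sqrt(1/15 + 1/7 + 1/75 + 1/35) = 0.501. For a 0.5 SD interaction, 0.5/0.501 - 1.96 = -0.96, so two-sided power is about 17%. It is 8% at 5% prevalence and 23% at 30%.

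**The case against.** The sentence in 3.0 is background, hemorrhage is an example in parentheses, and no endpoint in 2.0 mentions it. The wider aim of finding a scenario that favors one test is served, in exploratory form, by the four subcohorts. All of that stands, and it keeps the point small.

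Three stronger readings are tempting, and the documents do not support them.
- *Hemorrhage is an established effect modifier.* The pilot dropped two DSC patients, called the improvement slight, tested no interaction and gave no PET AUC after the exclusion. It never shows that the gap between PET and MRI changed.
- *The goal cannot be answered.* Nothing excludes hemorrhagic lesions and MRI is a protocol scan, so status could be coded later. That analysis would be unplanned and imprecise, not impossible.
- *Section 11.2 contradicts the interaction test in 1.0.* Section 11.2 is brief, but 1.0 and 11.3 together provide for a test and a regression across subcohorts. What is missing is hemorrhage among the groups.

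It is also fair to say that DCE and the ROI rule address hemorrhage in part by design, and that 3.1.2 and 3.2 give other reasons for DCE: spatial resolution, bone/air interfaces and absolute measurements. But the premise about hemorrhage is then left untested, which is a reason to look.

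Finally, the added subgroup would be weak, and the pilot's prevalence may not transfer: all 12 pilot patients had resection, against 15-25% expected to have surgery or biopsy here. That is true, and it limits what may be claimed. Imprecision alone does not disqualify an exploratory analysis in this plan: 11.1 provides for one expecting 5-10 anti-angiogenic patients, and 11.3 accepts that subsets may be too small for significance.

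**Conclusion.** The point holds as a gap between a named example and the analysis plan. Section 3.0 singles out hemorrhagic lesions and 3.2 relies partly on DCE being unaffected by them, but no recorded variable, subcohort or covariate lets the planned analysis address either. The primary comparison, its power and its error control are untouched. This is a cheap improvement, not a flaw in the main design.

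Closing the gap would yield an exploratory estimate only. The precision in the working rests on assumed prevalence, on AUCs of 0.8 and on an assumed correlation between the two tests. Even at the pilot's prevalence, an interval of plus or minus 0.20-0.25 would leave moderate differences unresolved. A null result should not be read as showing that hemorrhage does not matter.

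**What to change.** Define a hemorrhagic lesion in advance. Section 4.2.1 tells readers to avoid hemorrhage when placing ROIs but neither defines nor records it. Record status yes/no for each lesion from the protocol MRI, blinded to outcome, and add the field to 7.1.

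Add hemorrhagic versus non-hemorrhagic to 11.2 as an exploratory subgroup. Apply the interaction test promised in 1.0 to PET AUC minus MRI AUC by hemorrhage status, with the PET and MRI metrics named beforehand. Use a bootstrap that resamples patients, so that several lesions from one patient stay together. Report the counts by outcome, the estimate and its interval, with no confirmatory claim.

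The cost is a written definition, one lesion-level field and one analysis. The downside is one more low-precision exploratory subgroup. If the investigators do not want it, removing the hemorrhage example from the goal would align 3.0 with 11.2, though the DCE premise would remain untested.

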3.1 MRI

Conventional MRI provides exquisite high resolution images and detailed structural information about the size, location and effects of a tumor on the surrounding brain. When evaluating patients who have undergone radiation therapy, however, lesion size and enhancement characteristics are of relatively limited utility in distinguishing tumor

progression from radiation necrosis⁸, both of which can present as enhancing mass lesions on conventional MRI.^{9, 10} Enhancement in these cases reflects disruption or absence of the normal blood-brain barrier,^{9, 10} and does not necessarily correlate with residual or progressive tumor. Furthermore, contrast enhancement alone will likely become a less reliable marker with the increasing use of anti-angiogenesis agents such as Avastin (bevacizumab) that directly induce rapid and profound decreases in tumor enhancement.

